6. GENERAL ANALYSIS DEFINITIONS

6.1 TREATMENT

For basic study information on the treatment to be administered, assignment to treatment, and selection of dose, refer to CTP Section 4.

There are three treatment study phases in this trial: screening, double-blind study treatment phase (with avenciguat and matching placebo), and follow-up.

Table 6.1: 1 Flow chart of analysis phases

Label	Interval	Start date	End date
Screening	Screening	Date of informed consent	Date of first administration of double-blind study medication - 1
Placebo/ Avenciguat 2mg/ Avenciguat 3mg	On-treatment	Date of first administration of double-blind study medication	Date of last intake of study medication + X*,
Follow-up*	Follow-up	Date of last intake of study medication + X* + 1	Latest of (date of EOS visit, last contact date on EOS page)

*X=3 or REP (7 days) for safety laboratory and AE respectively. Follow-up phase might not be displayed, e.g., if the patient's trial termination date is within 7 days after last administration of study drug.

For efficacy analyses of HVPG, data up to REP+1 (8 days) after last treatment intake will be considered as on-treatment, because an HVPG measurement at EOT is permitted within 7 days after scheduled EOT (i.e., REP+1 day after last dose) as stated in Section 5.1.1 of the CTP.

The efficacy analyses will follow the intention-to-treat (ITT) principle in assigning patients to treatment groups, i.e., patients will be analysed in the treatment group they were randomized to.

AEs with an onset during the time of the incorrect study treatment will be listed separately.

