The combination of BI 685509 with other compounds involved in the NO-sGC-cGMP pathway, such as NO-donors (e.g. nitrates), phosphodiesterase (PDE)-5- inhibitors, non-specific PDE inhibitors and sGC-simulators might further increase the risk for hypotensive episodes and potentially reactive HR increases and the severity of these effects. Based on *in-vitro* data, BI 685509 is a weak inactivator of CYP3A4 and CYP2C8. A Drug-Drug Interaction (DDI) potential with CYP3A4 substrates cannot be excluded as BI 685509 is predicted to be a weak CYP3A4 inactivator. DDI threshold dose for CYP2C8 inactivation for the CSPH indication is close to the clinically relevant dose tested in Phase II. Thus, in addition to close monitoring of AEs among patients taking CYP3A4 narrow therapeutic index / or sensitive substrates, CYP2C8 and CYP3A4 narrow therapeutic index / or sensitive substrates will also be monitored to support patient safety. Inhibitors or inducers of UGT (uridine glucuronyl transferase) enzymes (especially UGT1A1) may potentially impact BI 685509 exposures in a clinically relevant manner. BI 685509 is a substrate of P-gp (permeability glycoprotein) and OATP (organic anion transporting polypeptide)1B1/3 transporters. Co-administration of single doses of BI 685509 and the P-gp inhibitor itraconazole increased BI 685509 C_{max} approximately 1.35-fold and AUC_{0-tz} approximately 1.55-fold, which is considered not clinically relevant. OATP1B1/3 inhibition by rifampicin increased the exposure of BI 685509 after co-administration of single doses approximately 2.15-fold for C_{max} and 2.74-fold for AUC_{0-tz}, which is considered clinically relevant. Thus, OATP1B1/3 inhibitors will be restricted (refer to Table [1.4.2: 1](#) and Section [4.2.2.1](#)).

Residual Effect Period

The Residual Effect Period (REP) of BI 685509 is 7 days. This is the period after the last dose with measurable drug levels and / or pharmacodynamic (PD) effects still likely to be present.

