6.7 BASELINE, TIME WINDOWS, AND CALCULATED VISITS

Regarding efficacy and safety endpoints, the term “baseline” refers to the last observed measurement prior to administration of any randomized study medication.

Measurements taken prior to the first intake of randomized study medication will be considered pre-treatment values. Pre-treatment values will be assigned to a visit according to the nominal visit number as recorded on the eCRF or as provided by the laboratory.

In general, the date of the first drug administration will be used to separate pre-treatment from on-treatment values. Measurements taken after first trial medication intake will be considered on-treatment values if they have been obtained up to end of the parameter-specific follow-up period as defined in Table [6.1:1](#) below and will be assigned to the randomized study medication for efficacy analyses and to the first study medication taken for safety analyses.

Measurements taken after the end of the endpoint specific follow-up period will be considered post-treatment values.

Table 6.7:1 Endpoint specific follow-up period for the assignment to treatment phase

Endpoint	Last day of assignment to treatment phase (Days after study medication stop date)
Efficacy	
HVPG	8
[REDACTED]	
Safety	
Adverse events	7
Safety laboratory measurements	3
Vital signs (including body weight, blood pressure)	1

For derivation of the last value on treatment, minimum value on treatment, and maximum value on treatment, all values from the relevant phase (whether or not collected in any time window; see Table [6.1:1](#) for definition of the trial phases) will be considered; these will be derived for analysis of laboratory and vital signs data.

On-treatment efficacy, safety [REDACTED] measurements will be assigned to visits based on the extended time windows around the planned visit dates, defined relative to the day of first trial medication intake (see Table [6.7:2](#)).

For the analyses of the secondary and further safety endpoints at week 8, the actual V7 date + X days (X=3 or 7 days for safety laboratory and AE respectively) will be used for the analysis time windows.

Table 6.7:2 Time windows for assignment of measurements to visits for statistical analysis

Visit number /name	Visit label	Planned day	Time window (Days)				
			Window (per CTP)	Start (per CTP)	End (per CTP)	Start (extended) *	End ^A (extended) *
V1	Screening	-42	+7			-∞	0
On-treatment							
V2	Week 0	Day 1	N/A	1	1	≤1	1

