V3	Week 1	Day 8	+2	8	10	2	11
V4	Week 2	Day 15	[contact]
V5	Week 4	Day 29	[contact]
V6	Week 6	Day 43	±3	40	46	37	50
V7	Week 8	Day 57	±3	54	60	51	71
V8	Week 12	Day 85	±5	80	90	72	99
V9	Week 16	Day 113	±5	108	118	100	127
V10	Week 20	Day 141	±5	136	146	128	155
V11	Week 24/ EoT	Day 169	±5	164	174	156	Study medication stop date + X [#] days
Off-treatment							
V12	Week 28/ EoS	Day 197	±5	192	202	Study medication stop date + X [#] days	Day of last follow-up value days +1

^A In case of premature discontinuation of the study medication, an early EoT visit has to be performed within 7 days of medication stop date. If such an EoT Visit falls into the time window of a previous visit, measurements will be assigned to this previous visit and the visit value will be determined as described above. In this case, the time window for the visit that includes the early EoT visit will end X days after the study medication stop date, including Day X. Patients will then be asked to continue in the study according to the visit schedule. Off-treatment measurements will be assigned to visits in the same manner.

Days are counted relative to the day of first treatment, which is defined as Day 1.

* Start (extended): End of extended window of last visit+1

End (extended): Midpoint of planned days between current visit and next visit

#X= 3 days for safety laboratory; X=1 day for biomarkers and vital sign, respectively; X= 8 days for HVPG and Fibroscan data.

The midpoint between two on-treatment visits defines the end of a time window, with the midpoint being included in the time window of the preceding visit. The end of the time window of the last on-treatment visit (end of treatment (EoT)) is endpoint dependent (Table 6.7:1).

Repeated and unscheduled efficacy and safety measurements will be assigned to the nominal visits and listed in the subject data listing according to the time windows described above. Only one observation per time window will be selected for analysis at an on-treatment visit - the value which is closest to the protocol planned visit day will be selected. If there are two observations which have the same difference in days to the planned day, the first value will be selected. If there are two observations on the same day, the first value will be selected. If there

are multiple values within the time window of the last visit, including a value on the last day of drug intake, the value on the last day of drug intake is used as the value of the last visit.

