To support analyses of liver related adverse drug effects, the frequency of patients with AST and/or ALT $\geq 3\times$ ULN combined with the total bilirubin $\geq 2\times$ ULN in a 30-day period after AST/ALT elevation will be displayed, stratified by alkaline phosphatase $< 2\times$ ULN and $\geq 2\times$ ULN (a patient can potentially be in both alkaline phosphatase strata in case of multiple AST/ALT and bilirubin elevations). The start of the 30-day time span is triggered by each liver enzyme elevation above defined thresholds. This analysis will be based on standardised laboratory values.

A graphical analysis of the ALT and total bilirubin during the on-treatment period will also be performed; the so called eDISH plot. In the graph, for each subject, the peak total bilirubin is presented as a fold increase over the ULN against the peak ALT as a fold increase over the ULN, on a log 10 scale. The measurements displayed or total bilirubin and ALT may, or may not, occur on the same date. Two reference lines, 2xULN for total bilirubin and 3xULN for ALT, are drawn onto the graph to divide the plane into four quadrants. Normal cases are in the lower left quadrant, potential DILI cases are in the upper right quadrant (Hy's Law quadrant), while the lower right quadrant is known as the Temple's corollary range (ALT $\geq 3\times$ ULN and total bilirubin $< 2\times$ ULN). The same graphical analysis will be repeated on AST and total bilirubin. Details on patients with elevated liver enzymes will be listed.

Clinically relevant findings in laboratory data will be reported as baseline conditions (at screening) or as AEs (during the trial). If judged clinically relevant by the investigator and will be analysed as such.

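### The SAP closes the on-treatment window for safety laboratory values 3 days after last intake, although the early-discontinuation visit that supplies the sample may fall up to 7 days after stopping

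*SAP*

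**What the plan says.** - **Laboratory window.** The footnote to SAP Table 6.1:1 defines the days added to last intake as "X=3 or REP (7 days) for safety laboratory and AE respectively". Table 6.7:1 repeats 3 days, and so does the footnote to Table 6.7:2: "X= 3 days for safety laboratory". The SAP gives no reason for the figure.
- **Early stoppers.** Footnote A of Table 6.7:2 notes that after premature discontinuation "an early EoT visit has to be performed within 7 days of medication stop date". It then says that "the time window for the visit that includes the early EoT visit will end X days after the study medication stop date, including Day X".
- **Values after the window.** SAP 6.7: "Measurements taken after the end of the endpoint specific follow-up period will be considered post-treatment values".
- **REP.** Protocol 1.2.1 sets it at 7 days and explains: "This is the period after the last dose with measurable drug levels and / or pharmacodynamic (PD) effects still likely to be present".
- **ED visit.** Footnote 3 of the protocol Flow Chart places it within 7 days of stopping; Sections 3.3.4.1 and 6.2.2.1 call this ideal timing. The Flow Chart marks safety laboratory sampling at EoT / ED, and the readable exceptions in Section 6.2.2.1 do not waive it (two are redacted).
- **Outputs.** SAP 6.7 takes last, minimum and maximum on-treatment values from the relevant phase only. SAP 7.8.2 builds its reference-range and change tables on the last on-treatment value, and describes the eDISH plot thus: "A graphical analysis of the ALT and total bilirubin during the on-treatment period will also be performed". The separate combined table counts patients whose bilirubin elevation accompanies a transaminase elevation, "in a 30-day period after AST/ALT elevation will be displayed", with no treatment-phase limit stated.

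**The concern.** The SAP states the 7-day allowance for the visit and, in the same footnote, closes the laboratory window at day 3. A site can follow the protocol exactly and still produce a sample that the main laboratory summaries ignore. For a patient who stops early, the ED sample is the one scheduled laboratory measurement soon after the last dose.

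The windows also differ between linked data. A hepatic AE on day 5 after the last dose is on-treatment; the laboratory values behind it are not. For HVPG, SAP 6.1 set 8 days expressly so that a measurement the protocol permits would count. The same reasoning was not applied to laboratory values.

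At stake is the completeness of the descriptive safety outputs for early stoppers, in particular transaminase or bilirubin values that peak after day 3.

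**Working it through.** No power or sample-size figure is involved, so this is a comparison of day counts.

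**Inputs**
- Laboratory window: X = 3 days (SAP Tables 6.1:1, 6.7:1, 6.7:2)
- AE window and REP: 7 days (SAP 6.1; protocol 1.2.1)
- ED visit: days 1 to 7 after last dose (protocol Flow Chart, footnote 3)
- Completers' last dose: the evening before EoT (same footnote), so the sample is on day 1
- Terminal half-life: 9 to 15 hours (protocol 1.2.1)
- Randomised patients: 78 (protocol 7.5)

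**Step 1: permitted ED days outside the window.** Days later than 3 are 4, 5, 6 and 7, which is 4 of 7 permitted days (4/7 = 57%). This is a share of days. It becomes a share of samples only if visits are spread evenly over the week, which is an assumption.

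**Step 2: completers.** Day 1 ≤ 3, so no EoT sample is lost.

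**Step 3: patients, under assumptions only.** With even timing and an assumed early-stopping rate across all arms:
- 5%: 78 × 0.05 × 4/7 = 2.2 patients
- 30%: 78 × 0.30 × 4/7 = 13.4 patients

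This gives roughly 2 to 13 patients. The true count could be lower or higher, depending on visit timing and the discontinuation rate.

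**Step 4: very early stoppers.** Suppose a patient stops before Visit 3, the first scheduled post-baseline sample, and has the ED visit on days 4 to 7. Unless an unscheduled sample was taken, that patient may have no on-treatment value. SAP 7.8.2 analyses a parameter only in patients with at least one on-treatment value, so this patient leaves the analysis of that parameter.

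**Step 5: is there a pharmacokinetic reason for 3 days?** Five half-lives are 5 × 9/24 = 1.9 days to 5 × 15/24 = 3.1 days. The fraction left at 72 hours is 0.5^(72/9) = 0.4% to 0.5^(72/15) = 3.6%. A 3-day window could be argued on drug levels, but the SAP does not make that argument, and the protocol's REP also covers pharmacodynamic effects.

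**Step 6: after the change.** With X = 7, 0 of the 7 permitted days fall outside. ED visits after day 7, which the word ideally leaves possible, would still be post-treatment.

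**The case against.** **The window may be deliberate.** SAP Table 6.7:1 uses endpoint-specific windows (vital signs 1 day, laboratory 3, AEs 7, HVPG 8). Protocol 7.2.6 ties the REP to AEs and sets no laboratory window. This stands in part: a reader might infer that the SAP contradicts a protocol rule, and it does not. What remains is an unexplained mismatch with a practical consequence.

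**The liver signal is mostly kept.** The rise that leads to stopping is normally measured before or around the stop, so it stays in the window. Protocol Appendix 10.2 asks for repeat testing within 48 to 72 hours, which generally also falls within 3 days if drug is stopped at the rise. A patient stopped under the combined transaminase and bilirubin rule already has both values. This stands. Only values after day 3 are exposed, although Appendix 10.2 lets such patients complete EoT procedures after resolution or stabilisation, so later values will exist.

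**There are backstops.** All individual laboratory data and details of patients with elevated enzymes are listed. Clinically relevant findings become AEs with a 7-day window, and hepatic events are adjudicated and tabulated. The combined transaminase-bilirubin table has no stated on-treatment limit. This also stands. But listings do not replace the summaries and plots in which arms are compared, and the reach of the combined table is left to interpretation.

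**Bias is not shown.** A reader might infer that an arm with more stopping will look cleaner. The documents do not support this: ED values may be falling, earlier on-treatment peaks are retained, and discontinuation by arm is unknown.

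**Conclusion.** The point holds as a limited gap in the SAP's laboratory summaries. ED samples that comply with the protocol are excluded on 4 of the 7 permitted days, from named outputs, for early stoppers only. A very early stopper may leave a parameter's analysis altogether.

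The 57% should not be read as a loss rate for samples, and the range of 2 to 13 patients rests wholly on assumed stopping rates and even visit timing. Nor do the documents show that drug-induced liver injury would go unseen. The exposure is confined to ED or later peak values after day 3, with no demonstrated direction between arms. All analyses in this trial are descriptive, so no test result is affected. This is a cheap improvement worth making.

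**What to change.** 1. In SAP 6.1 (Table 6.1:1 footnote), Table 6.7:1 and the Table 6.7:2 footnote, set the safety laboratory window to the 7-day REP already used for AEs. Apply the same figure to the Week 8 laboratory rule in SAP 6.7, which also uses 3 days, or say why it differs.
2. In SAP 7.8.2, state that the combined ALT/AST-bilirubin table uses its full 30-day look-forward regardless of treatment phase.
3. Optionally, show transaminase and bilirubin values after the REP in a separate, clearly marked supplementary display. This need not be part of the main eDISH plot, because values long after the last dose may reflect disease progression.

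The cost is SAP wording and one programming constant; no new data are needed. The downside is that some values taken at low or no drug levels count as on-treatment and may become a patient's last on-treatment value. ED visits after day 7 still fall outside.

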6.2 IMPORTANT PROTOCOL DEVIATIONS

Protocol deviations (PD) must be assessed to determine whether it is an important Protocol Deviation (iPD). The documentation of the iPD categories and how to handle iPDs in the analysis are done in the DV domain.

Handling of iPDs in analysis is included in the DV domain specifications and stored within the TMF in EDMS.

The decision about which PD could generate exclusion from analysis sets will be taken during the study and finalized at the last report planning meeting (RPM), i.e., before unblinding.

Non-important COVID-19 related PDs will only be listed.

[figure not shown]
6.3 INTERCURRENT EVENTS

The expected intercurrent events (ICEs) of interest in this trial are:

- Use of the following restricted concomitant therapy:
 - NO-sGC-cGMP pathway activating therapies like NO-donors (e.g. glyceryl trinitrate, isosorbide di- or mono-nitrate, molsidomine), PDE-5-inhibitors (e.g. sildenafil, tadalafil, and vardenafil), non-specific PDE inhibitors such as dipyridamole and theophylline, or sGC-stimulators (e.g., riociguat)
- New onset of / dose change in existing NSBB / carvedilol,
- Occurrence of a decompensation event
- Premature discontinuation of assigned trial medication.

The identified ICEs based on medical review will be confirmed before the DBL.

As a **primary estimand**, the **Hypothetical strategy** will be used for handling these intercurrent events for primary objective as a main analysis as if all the intercurrent events had not happened.

[figure not shown]
[figure not shown]
[figure not shown]

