2. TRIAL OBJECTIVES AND ENDPOINTS

2.1 MAIN OBJECTIVES, PRIMARY AND SECONDARY ENDPOINTS

2.1.1 Main objectives

The trial will compare two doses of BI 685509 (██████████ and ██████████ *BID*) with placebo, on top of standard of care, in patients with CSPH in compensated alcohol-related cirrhosis. The primary objective is to estimate the mean difference between treatment groups with placebo in percentage change in HVPG from baseline measured after 24 weeks. The primary treatment comparison will be made for treated patients with baseline HVPG measurements (Full Analysis Set, FAS) as if all patients took randomised treatment for the duration of the trial. Safety and tolerability will also be investigated.

[figure not shown]

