4.1.4.1 Rules for down-titration in case of intolerance to trial medication

If a patient has an AE that, based on Investigator judgement, may be related to trial medication, the down-titration rules below must be followed. These rules apply if the patient has successfully completed the dose titration period (i.e. Visit 4) and is either still taking their assigned dose of trial medication, or if they have missed ≤ 3 consecutive doses³. If the patient has not successfully completed the dose titration period (i.e. Visit 4), down-titration is not permitted; in case of persistent AEs or severe effects, the patient must permanently discontinue treatment (refer to Section 3.3.4.1).

- if the patient is currently receiving either [REDACTED] BID BI 685509 or [REDACTED] BID 685509 (or corresponding matching placebo) the dose will be down-titrated one level i.e.
 - [REDACTED] BID BI 685509 / matching placebo down-titrates to [REDACTED] BID BI 685509 / matching placebo
 - [REDACTED] BID BI 685509 / matching placebo down-titrates to [REDACTED] BID BI 685509 / matching placebo

Once down-titration has taken place, no further up-titration will be permitted.

³One dose refers to an individual time point e.g. morning dose or evening dose.

If a patient continues to have an AE, or a new AE develops, that based on Investigator judgement, may be related to trial medication, a second down-titration will be permitted. Depending on the randomisation assignment, this may be a pseudo down-titration i.e.:

- if the patient is currently receiving [REDACTED] BID BI 685509 or matching placebo the dose will be down-titrated to [REDACTED] BID BI 685509 matching placebo (a patient previously down-titrated to [REDACTED] BID BI 685509 matching placebo will be pseudo down-titrated)
- if the patient is currently receiving [REDACTED] BID BI 685509 or matching placebo the dose will be down-titrated to [REDACTED] BID BI 685509 / matching placebo

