7.2.2 Handling of intercurrent events

The expected intercurrent events of interest in this trial are:

- use of the following restricted concomitant therapy:
 - NO-sGC-cGMP pathway activating therapies like NO-donors (e.g. glyceryl trinitrate, isosorbide di- or mono-nitrate, molsidomine), PDE-5-inhibitors (e.g. sildenafil, tadalafil, and vardenafil), non-specific PDE inhibitors such as dipyridamole and theophylline, or sGC-stimulators (e.g. riociguat)
- new onset of / dose change in existing NSBB / carvedilol concomitant therapy
- occurrence of a decompensation event

All intercurrent events will be handled according to the hypothetical approach as defined in ICH E9 (R1), to perform treatment comparison as if all patients took randomised treatment. Each analysis will reference the strategy for handling intercurrent events that it will be estimating. The estimand for each main analysis in this CTP is the combination of the relevant detailed clinical objective from Section [2.1](#) and this strategy.

Handling of the intercurrent events that are not listed above will be decided by the blinded review and will be documented in the TSAP.

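### Does SAP 6.3 need a separate intercurrent event for a low-dose patient whose second down-titration may end on matching placebo?

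*SAP*

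**What the plan says.** Protocol 2.1.1 sets the primary comparison in the full analysis set "as if all patients took randomised treatment for the duration of the trial". Protocol 7.2.2 applies the hypothetical approach "to perform treatment comparison as if all patients took randomised treatment" and names three events: restricted NO-sGC-cGMP therapy, new or changed NSBB/carvedilol, and decompensation. For the rest it says: "Handling of the intercurrent events that are not listed above will be decided by the blinded review and will be documented in the TSAP".

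SAP 6.3 repeats those three and adds a fourth, "Premature discontinuation of assigned trial medication". All four are handled hypothetically for the primary estimand; the chosen approach "will be used for handling these intercurrent events for primary objective as a main analysis as if all the intercurrent events had not happened". On identification it says: "The identified ICEs based on medical review will be confirmed before the DBL".

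Protocol 4.1.4.1 allows two reductions after the titration period. "Once down-titration has taken place, no further up-titration will be permitted". For the second reduction, one bullet reads "the dose will be down-titrated to [REDACTED] BID BI 685509 matching placebo (a patient previously down-titrated", and its bracket calls the step a pseudo step for someone already on placebo. The companion bullet puts a slash between the drug name and matching placebo.

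SAP 6.1 counts HVPG as on-treatment up to 8 days after the last intake of study medication and analyses patients as randomised. SAP 7.5.2 restricts the Week 8 ANCOVA to on-treatment HVPG. SAP 7.7 plans a listing of patients who switched treatment by down-titration, with exposure to each treatment.

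**The concern.** If the missing slash is deliberate, a low-dose patient who needs two reductions ends on placebo tablets and cannot be up-titrated again. Active drug has stopped, but study medication has not. Read literally, the on-treatment rule in SAP 6.1 then keeps later HVPG values in the low-dose arm, because placebo tablets are study medication. A low-dose patient who stops all tablets has an intercurrent event, and Protocol 6.2.2.1 requires no HVPG at the early discontinuation visit. A patient moved to placebo goes on to the scheduled HVPGs. Two patients in the same pharmacological position could therefore be handled in opposite ways, against an estimand that supposes everyone took randomised treatment.

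The effect would fall on the low-dose estimate and on the comparison of the two doses. A high-dose patient's second reduction appears to end on active drug, so the same question does not arise there.

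**Working it through.** **1. Is the placebo endpoint established?** Three features bear on it.

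- The missing slash favours placebo.
- The pseudo bracket refers to a patient already on placebo, which also favours it. It would equally fit a dropped slash.
- Protocol 4.1.1 lists three active strengths, and Protocol 3.1 starts all patients on a common dose, so no listed active level lies below the start. This fits either reading: the next step is placebo, or there is no lower level and the patient stays on the starting dose as a pseudo step.

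Placebo is the likelier reading, but the redaction prevents certainty.

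**2. Does the SAP already have a place for it?** The fourth item in SAP 6.3 speaks of the assigned medication. A low-dose patient receiving only placebo no longer takes it. Protocol 7.2.2 sends unlisted events to blinded review, and SAP 6.3 has events confirmed before lock. Some material after the primary-estimand sentence in SAP 6.3 is not shown in the public copy. No visible rule says that the transfer is not an intercurrent event.

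**3. Reproducing the plan's own figure.** From Protocol 7.5: mean reductions 0, 23 and 25%, SD 27.5%, 26 per arm, correlation 0.2 between the active groups, threshold 15 points.

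- SE of a contrast with placebo = 27.5 × √(2/26) = 7.63.
- Correlation of the two contrasts = (1 + 0.2)/2 = 0.6, taking 0.2 as the correlation between the active group means.
- P(at least one dose ≥ 15) from the bivariate normal = 95.2%, against 94.95% stated.

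**4. Size if the values are kept.** Let k low-dose patients of 26 be on placebo at Week 24 with the whole effect lost. The counts are assumptions.

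- Low-dose contrast = 23 × (1 − k/26). One patient costs 23/26 = 0.88 points, and 0.88/7.63 = 0.12 SE.
- P(low ≥ 15) = Φ((contrast − 15)/7.63).
- P(at least one ≥ 15) holds the high dose at 25.

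| k | Low-dose contrast | P(low ≥ 15) | P(at least one ≥ 15) |
|---|---|---|---|
| 0 | 23.0 | 85.3% | 95.2% |
| 1 | 22.1 | 82.5% | 94.7% |
| 2 | 21.2 | 79.3% | 94.2% |
| 3 | 20.3 | 75.8% | 93.7% |
| 5 | 18.6 | 68.0% | 92.8% |

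The last column is the protocol's planning criterion. It moves by 0.5 to 2.4 points.

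**5. Would removing the values be better?** Compare root mean square error (RMSE) with the values kept against the SE with them removed.

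- SE if removed = 27.5 × √(1/(26 − k) + 1/26). This is unbiased only under missing at random, and it ignores any recovery of information from Week 8.
- RMSE if kept = √(SE² + bias²), with p = k/26, d the part of the 23-point effect that is lost, bias = d × p, and low-arm variance 27.5² + p(1 − p)d².

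| k | SE if removed | RMSE kept, all effect lost (d = 23) | RMSE kept, half lost (d = 11.5) |
|---|---|---|---|
| 1 | 7.70 | 7.73 | 7.65 |
| 2 | 7.78 | 7.92 | 7.70 |
| 3 | 7.87 | 8.20 | 7.78 |
| 5 | 8.07 | 8.99 | 7.99 |

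With the whole effect lost, removal is about level at one patient and better from two. With half retained, keeping has the smaller RMSE at every count shown. With a quarter retained (d = 17.25), keeping is slightly better at one patient (7.68 against 7.70) and level at two. Partial persistence is conceivable, since Protocol 1.2.1 posits an anti-fibrotic action, but the documents do not quantify it.

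**The case for a change.** The best case for a change is that the placebo reading is the more natural one, that Protocol 7.2.2 promised unlisted events would be documented in the TSAP, and that the visible final TSAP does not mention this one. A literal programmer following SAP 6.1 would keep the values. One sentence and one flag from the IRT records would settle it, with the rule fixed before unblinding and true transfers identified only afterwards.

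Part of this stands. The visible text does not name the transfer, and with five transfers the low-dose estimate would lose 4.4 points (23 × 5/26), which matters in a trial whose purpose is estimation.

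Two things weaken it. First, the proposed main-analysis rule would delete values in the low-dose arm only, after a step triggered by a possibly drug-related adverse event, while keeping values after the same apparent step in the placebo arm. That depends on missing at random where the assumption is doubtful. Blinded review could flag second reductions, but it could not say which were true transfers without revealing the arm. Second, the number of transfers is unknown. A patient must complete titration and then have adverse events leading to two reductions. Protocol 1.2.3 reports that orthostatic intolerance in Trial 1366-0020 occurred in the higher dose groups, led to no discontinuation and recovered on continued treatment. Five of 26 has no basis in the documents.

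**Conclusion.** No change to the plan follows. This is a gap in wording that analysts can fill from the text they have: the assigned-medication item, the stated aim of the comparison and the review before database lock all support treating a confirmed transfer as discontinuation of the assigned drug. Any such transfers would appear by patient in the SAP 7.7 listing.

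Forcing a removal rule into the main analysis is a trade-off with no assured gain. It helps if the whole effect is lost and missing at random holds, and it does not if half the effect persists. The size is 0.88 points (0.12 SE) on the low-dose contrast per transfer, and 0.5 to 2.4 points on the at-least-one-dose probability for one to five transfers.

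These figures rest on the protocol's 23/25/0 scenario with SD 27.5%, on assumed transfer counts, and on the placebo reading of Protocol 4.1.4.1, which only the sponsor can confirm. If the second step instead leaves the patient on the starting dose, there is no transfer to placebo and the point falls away. Nothing here bears on the titration rule itself.
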